6.0. Treatment plan

6.1 Talimogene laherparepvec injection

Talimogene laherparepvec will be given via intra-tumoral injection at visible locally recurrent breast cancer site and skin metastases if indicated at an initial dose of 10^6 PFU/mL for all sample size of 35. If patient has multiple lesions the lesion selection as the following:

- 1) If the largest lesion is > 5 cm, only this lesion will be used for injection;
- 2) If the largest lesion is < 5.0 cm, we will prioritize the size of the lesions (from large to small), and administer talimogene laherparepvec based on injection guideline in Table 3 below. The maximum dose of each course should not exceed 4.0 mL.
- 3) If patients do not have distant metastases, the lesion of lowest priority for injection should be left uninjected at least until it is biopsied.

The injection dose will not be affected by patients' actual body weight. The second talimogene laherparepvec dose will be administered 10^8 PFU/mL on day 22, and talimogene laherparepvec will be administered every 2 weeks after the second course with same dose with the maximum dose of 4.0 mL for each course (Figure 4). The injection dose varies according to the tumor spread area and using the talimogene laherparepvec injection volume guideline based on tumor size (Table 3). Distribution of the injection to separate sites will be permitted if the lesion is more than 5.0 cm diameter and/or multiple lesions. When disease diameter is greater than 5.0 cm and difficult to inject uniformly, we divide disease location tetrameric injection site with 1.0 mL administration each. On each treatment day, injections should be prioritized as follows:

[figure not shown]
- any new injectable tumor that has appeared since the previous injection
- by tumor size, beginning with the largest tumor and then the second largest tumor if agent available, otherwise treat in the following courses
- by tumor size, when similar size tumor exist, prioritize one and then the other tumor if agent available, otherwise treat in the following courses
- by tumor size, when huge tumor exist (greater than 10.0 cm), inject talimogene laherparepvec at different site for aiming uniform distribution in the following course.
- any previously uninjectable tumor(s) that is now injectable

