Within the guidelines of the algorithm in Table 3 and the prioritization model above, each lesion should be injected with the maximum amount possible at each visit before moving on to the next lesion, subject to tumor-specific limitations (such as the inability to inject the full amount into the lesion). Lesions should be injected until the maximum volume per day (4.0 mL) has been reached or there are no further injectable lesions, whichever comes first.

Lesion site preparation

- Talimogene laherparepvec is to be administered only by intralesional injection into cutaneous, subcutaneous and nodal lesions with or without image ultrasound guidance. Talimogene laherparepvec must not be administered into visceral organ metastases.
- The injection site may be pre-treated with a topical anesthetic agent or an injectable local anesthetic; however, a local anesthetic must not be injected directly into the lesion. Please note that the anesthetic should not be mixed together with talimogene laherparepvec in the same syringe. Talimogene laherparepvec does not require any routine premedication.
- Swab the lesion and surrounding areas with alcohol, allow to dry.
- Talimogene laherparepvec is administered by HCP

Figure 4: Timeline of talimogene laherparepvec injection

* Talimogene laherparepvec is administered lower dose for the first course due to possible sero-negative status.

** Biopsy from local disease.

*** Biopsy from distant metastases if available or local disease of non-injection site (optional)

[figure not shown]
Table 3. Talimogene laherparepvec injection volume guideline based on tumor size

Tumor Size (longest dimension)	Maximum Injection Volume
> 5.0 cm	4.0 mL
> 2.5 cm to 5.0 cm	2.0 mL
> 1.5 cm to 2.5 cm	1.0 mL
> 0.5 cm to 1.5 cm	0.5 mL
\leq 0.5 cm	0.1 mL

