8.0. Evaluation during study

The window for all assessments and treatments should be completed within 5 days of the scheduled time.

Patients will be allowed to continue current hormonal therapy, selected chemotherapy, targeted agents and/or anti-HER-2 therapy, which will be administered as standard of care, (per physician discretion) while receiving study drug.

8.1. Evaluation during talimogene laherparepvec:

- 8.1.1. Patients will have a CBC, differential count and platelet count before each cycle.
- 8.1.2. Patients may repeat the CBC, differential count and platelet count until recovery of these measures before the next cycle (absolute neutrophil counts \geq 1,000 and platelets \geq 100,000 per mm³).
- 8.1.3. Medical history and physical examination with vital signs, weight, and PS before cycles 2 and 5 and every additional 2 cycles of treatments.
- 8.1.4. Digital photography of chest lesions before cycles 2, 5, and every additional 2 cycles of treatment.
- 8.1.5. Toxic effects will be assessed before each cycle.
- 8.1.6. SMA (Na, K, BUN, creatinine, Mg, calcium, AST, ALT, glucose, LDH, and total bilirubin) will be performed before each cycle.
- 8.1.7. Levels of tumor markers (e.g., cancer antigen CA 27.29) will be assessed before cycle 5 and every additional 4 cycles of treatment.
- 8.1.8. Systemic immunity in serum or plasma levels of GM-CSF, IL-2, IL-12, TNF-alpha (α), IFN- alpha (α); and phenotype for T-cell subsets (CD3, CD4, CD8, CD25), and NK-cell subsets (CD16, CD56) will be determined via multiparameter FACS analysis (percentage and absolute numbers) before cycle 5 and at the end of study in [name] laboratory at MD Anderson.
- 8.1.9. PET-CT or CT of bone/ abdomen/chest should be performed before cycle 5 and before every additional 4 cycles of treatment as clinically indicated.
- 8.1.10. Disease assessment will be done at the end of cycle 4, cycle 8 and cycle 10.

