8.3 Study Calendar

Evaluation and treatment	Screening	Cycle 1 Day 1	Cycle 2 (D22+/-5 days)	Cycle 5 (D64 +/- 5 days)	Cycle 7 and every 2 cycles	Follow up⁹
Time	Baseline (within 6 weeks)	Prior to talimogene laherparepvec injection				
Eligibility, screening, consent, and registration	X					Patients will be monitored for 1 year after removal from the study or until death, whichever occurs first.
Medical history	X					
Staging with tumor measurements	X					
Photography of chest wall	X ¹		X	X	X	
Biopsy of local recurrence [HE, IHC]	X ⁸			X ⁸		
Biopsy of easily accessible distant metastasis [HE, IHC]				X ⁸		
Correlative immune study	X			X ⁷		
Physical examinations, vital signs	X	X ²	X	X	X	
ECOG PS	X	X ²	X	X	X	
Hematology assessment and Biochemical profiles ^{3,5}	X	X ²	X	X	X	
Tumor markers (CA27.29) ¹¹ , IgG (baseline only)	X			X	X ¹¹	
Chest X-ray; Breast sonography ¹³	X					
Pregnancy test if applicable ¹⁰	X					
PET-CT or CT scan of bone/abdomen/chest as clinically indicated	X			X	X ⁴	
Disease assessment ¹²				X	X	

Adverse events ⁵	X	X	X	X	X	
Talimogene Laherparepvec injection ⁶		X	X	X	X	

1. Within 1 week prior to treatment
2. No need to repeat if within 7 days from baseline
3. Hematology include CBC, differential count and platelet count; and biochemical profiles SMA include Na, K, BUN, creatinine, Mg, calcium, AST, ALT, LDH, total bilirubin
4. Repeat every 4 cycles as clinical indicated
5. Before each cycle. Reporting exposure to talimogene laherparepvec and should be collected for the duration of the study and safety f/u
6. Starting cycle 2, Talimogene Laherparepvec injection will be given every 2 weeks until disease progression
7. Correlative immune study will be repeated before cycle 5 and at the end of study if available.
8. Core biopsy of local recurrence at baseline if samples (i.e., paraffin block or 5-10 unstained slides) from the local recurrence are not available. Core biopsy of either distant metastasis or local recurrent lesions before cycle 5 based on patient status.
9. a. Safety Follow-Up: should be conducted approximately 30 days after the last dose of trial treatment or before the initiation of a new anti-cancer treatment, whichever comes first. Safety Follow-Up Visit can be done in the clinic, or by phone if patient is not willing to come to the clinic for follow up.
- b. Unexpected AEs: Patients removed from study for unexpected adverse events will be monitored until AE is resolved or stabilized.

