13.0. Statistical consideration

13.1. Statistical design

The primary objective of this phase II trial is to assess the efficacy of talimogene laherparepvec as a single agent in locally recurrent IBC and non-IBC patients. The primary endpoint is the rate of overall response.

The overall response rate is defined as the percentage of CR, PR in overall patients. Patients will be evaluated for disease control at the end of cycle 4 (2 months), cycle 8 (4 months) and cycle 10 (5 months). If patients have measurable disease only and achieve CR or PR, they will be considered Response Type I. If patients have non-measurable disease only, and achieved CR, they will be considered as Response Type II. If patients have both measurable and non-measurable disease and achieve CR or PR at the measurable disease sites, and achieved CR at the non-measurable disease site, they will be considered as Response Type III. If patients have mixed responses such as progression of measurable disease and no progression of non-measurable disease at 5 months or vice versa, they will be considered to have uncontrolled disease. The Overall Response rate will be defined as a sum of the 3 response types.

The trial will be conducted using a two-stage design and the overall response rate will be estimated accordingly. It is assumed that the talimogene laherparepvec single agent will have a response rate of 20%. A response rate of 5% or lower will be considered treatment failure and the regimen will be rejected under this circumstance. 13 patients will be enrolled to the first stage. The study accrual will be delayed until all 13 patients are evaluable for response. A summary report will be submitted to the medical monitor in the IND office. If no patients achieve an overall response to the treatment, the trial will be stopped and the regimen will be declared as ineffective. If there are 1 or more patients achieve an overall response, 22 more patients will be enrolled to the study to reach a total of 35 treated patients. By the end of the study, the new regimen will be rejected if less than or equal to 3/35 patients achieve overall response and will not be considered worthy of further investigation otherwise.

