We will monitor severe toxicity, grade 3 or greater possibly, probably or definitely treatment related toxicities with CTCAE ver.4.0, by cohorts of 5 patients for the whole patient population (N=36) for the first cycle. A summary report will be submitted to the medical monitor in the IND office. The stopping boundary is calculated based on the beta-binomial distribution. We assume that number of patients who develop severe toxicity follows a binomial distribution with probability p , and p has a prior distribution of beta (0.20, 0.80). We consider that the probability of severe toxicity greater than 20% is excessive to the patients. The stopping boundary is chosen to stop the trial if the data indicate that there is a high probability that excessive toxicity-i.e., probability $(p>0.20|data) \geq 90\%$. The trial will be stopped and the treatment will be considered too toxic if the number of patients with severe toxic effects exceeds $>=3/5, 4/10, 6/15, 7/20, 8/25, 10/30$, and $11/35$ for the first cycle. The operating characteristics are provided, based on 5,000 simulations. For example, if the true toxicity rate is 10%, the probability to stop the trial early due to toxicity is very low, 2% and an average of 34.5 patients will be treated on trial. On the other hand, if the true severe toxicity rate is 30%, the probability of stopping the trial early would be 62% with an average of 21.5 patients treated. When the true severe toxicity rate is 20%, we will have a 21% chance of terminating the trial early with an average of 30.3 patients treated. However if the toxicity rate is as high as 40%, then we will have a 91% chance to stop the trial early and with an average of only 13.5 patients treated.

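### The only numeric toxicity stopping rule counts cycle 1 alone, so severe events after the 10^8 PFU/mL injections from day 22 cannot trigger it

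*Combined protocol and SAP*

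**What the plan says.** Section 13.1 monitors possibly, probably or definitely related toxicity of grade 3 or higher "by cohorts of 5 patients for the whole patient population (N=36) for the first cycle". The rule is: "The trial will be stopped and the treatment will be considered too toxic if the number of patients with severe toxic effects exceeds" the listed counts of 3/5, 4/10, 6/15, 7/20, 8/25, 10/30 and 11/35, and that sentence again limits the count to the first cycle. The boundary uses a Beta(0.20, 0.80) prior and stops when the posterior probability of a rate above 20% reaches 90%. The stated chances of stopping early are 2%, 21%, 62% and 91% at true rates of 10%, 20%, 30% and 40%.

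Section 6.1 starts every patient at 10^6 PFU/mL. It continues: "The second talimogene laherparepvec dose will be administered 10^8 PFU/mL on day 22", with the same concentration every 2 weeks after that. The calendar in 8.3 labels day 22 as cycle 2 and day 64 as cycle 5. Section 6.5.1 plans at least 10 cycles. A note to Figure 4 explains the first dose: "Talimogene laherparepvec is administered lower dose for the first course due to possible sero-negative status". Section 13.1 gives no reason for the monitoring window.

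**The concern.** The conclusion that the rule can draw, that the treatment is too toxic, concerns the regimen. The data that feed it come from one injection out of at least ten, at one hundredth of the later concentration. If severe toxicity first appears at 10^8 PFU/mL, the boundary cannot respond, however many patients are affected. The operating characteristics may also reassure too widely: a 91% chance of stopping at a 40% rate is true only if the 40% occurs in cycle 1.

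**Working it through.** **1. Reproduce the plan's rule.** At each n = 5, 10, ..., 35, take the smallest x with P(p > 0.20 | Beta(0.2 + x, 0.8 + n − x)) ≥ 0.90. At n = 5, x = 3 gives 0.960 and x = 2 gives 0.797. All seven looks give 3, 4, 6, 7, 8, 10 and 11, as stated.

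An exact binomial recursion over the looks at 5 to 30, with a maximum of 35 patients and a stop at or above the listed count, gives:

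| True rate | Stop before n = 35 | Plan |
|---|---|---|
| 5% | 0.2% | not given |
| 10% | 2.0% | 2% |
| 20% | 20.8% | 21% |
| 30% | 61.1% | 62% |
| 40% | 90.6% | 91% |

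The plan's figures stand. The rate in the first column is the cycle-1 rate, because that is all the rule counts.

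**2. What the window contains.** Cycle 1 runs from day 1 to about day 21 and holds the 10^6 injection only. A window to the end of cycle 4 (before cycle 5 on day 64) would add three 10^8 injections, on days 22, 36 and 50.

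**3. Risk per 10^8 dose (assumed).** Let cycle 1 carry 5% and each 10^8 dose an independent risk r of a first severe event. The rate over cycles 1 to 4 is w = 1 − 0.95 × (1 − r)^3. With the boundary unchanged:

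| r | w | Stop, cycles 1 to 4 | Stop, as written |
|---|---|---|---|
| 2% | 0.106 | 2.4% | 0.2% |
| 5% | 0.1855 | 16.3% | 0.2% |
| 10% | 0.307 | 64.1% | 0.2% |

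A window to the end of cycle 2 only, w = 1 − 0.95 × (1 − r), gives 0.6%, 1.8% and 7.1%.

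**4. Even rise to a 10-cycle total (assumed).** With 5% in cycle 1 and 40% by cycle 10, the risk per cycle is h = 1 − (0.60/0.95)^(1/9) = 0.0498. The cycle 1 to 4 rate is 1 − 0.95 × (1 − 0.0498)^3 = 0.1849, and the stop probability is 16.1%. For totals of 20% and 30% it is 2.2% and 6.6%. Through cycle 8 the three figures are 11.9%, 40.3% and 74.3%.

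**5. Sensitivity to the limit.** The 20% limit was set for one injection. In the 40% case of step 4, using the step 1 formula with the prior mean matched to the limit:

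- limit of 25%: boundary 3, 5, 7, 8, 10, 11 at n = 5 to 30, stop probability 7.5%;
- limit of 30%: boundary 4, 6, 8, 9, 11, 13, stop probability 1.4%.

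**6. Keeping both sets of looks.** A cohort's cycle-1 count cannot exceed its count over the longer window. With the same boundary, the two sets together therefore stop exactly the trials that the longer window alone would stop, some of them sooner.

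**The case against.** A reader might infer that 13.1 contradicts 6.1. It does not: a first-cycle window is compatible with the dosing schedule, and the operating characteristics follow directly after the sentence that limits the boundary to cycle 1.

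A reader might also infer that toxicity at 10^8 PFU/mL goes unwatched. The documents say otherwise. Section 8.1 states: "Toxic effects will be assessed before each cycle". Sections 6.3.1, 6.3.3 and 6.4 set patient-level delays and discontinuation over the whole of treatment, and 11.2 sends all serious events to the IND Office. The stage 1 hold adds a review with a report to the medical monitor: "The study accrual will be delayed until all 13 patients are evaluable for response". Since "Disease assessment will be done at the end of cycle 4, cycle 8 and cycle 10", that hold falls after some 10^8 exposure. What remains is that none of these sets a toxicity count for the trial.

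Nor do the documents show that severe toxicity rises after cycle 1. In the phase 1 study (4.4.3), events of any grade followed the first, second and third injections in 27/30 (90%), 13/15 (87%) and 11/15 (73%) of patients. Reactions in patients who were seronegative at entry make a first-exposure window plausible. Those figures are not grade 3 or higher rates and mix dose levels, so they do not settle the question, but every rising scenario above is assumed.

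The remedy also has limits. Through cycle 4 the gain is modest unless toxicity is early or large, and it shrinks if the limit is raised for a longer window. Stating the reason and relabelling the figures would be cheaper and would make the scope clear, but would not change what the rule can detect.

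**Conclusion.** The point holds as a gap in scope; the plan's arithmetic is right. The only numeric trial-level toxicity rule covers the 10^6 PFU/mL injection and none of the 10^8 injections, and the published operating characteristics carry the same restriction. With a cycle-1 rate of 5% or 10%, the rule stops before patient 35 with probability 0.2% or 2.0%, whatever happens later.

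The benefit of a cycle 1 to 4 window ranges from small (2.4%) to substantial (64.1%) over 2% to 10% risk per 10^8 dose. This rests on an assumed 5% in cycle 1, constant and independent risk per dose, and an unchanged 20% limit. It should be fixed: the data are already collected and a pre-specified count is a specific safeguard. The case is for covering later exposure, and does not rest on evidence that later exposure is more toxic.

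**What to change.** Keep the cycle-1 looks as an early check. Add, at the same cohorts of 5, a count over one fixed window per patient that includes several 10^8 injections, for example day 1 to the end of cycle 4, which matches the first disease assessment. Count each patient once, take the look when the cohort has completed the window, and state how patients who leave early are counted. The sponsor should confirm the excessive-toxicity limit for that window, recompute the operating characteristics, and label each set by its window. If the cycle-1 window is kept alone, 13.1 should say why and label its figures as cycle 1 (10^6 PFU/mL) only.

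The cost is a protocol amendment during the trial and a recount, from existing data, of the 8 patients already treated. No new assessments are needed. Window-based looks come about 6 weeks later than cycle-1 looks (day 64 against day 22, 42 days). The documents give no accrual rate; at an assumed 1 to 3 patients a month, 42/30.4 × (1 to 3) is about 1 to 4 more patients enrolled before a look. Section 13.1 does not say whether accrual pauses at a look. If it does, the six looks from 5 to 30 could add up to 6 × 6 = 36 weeks, less any overlap with the stage 1 hold. For patients on schedule, that hold already allows the looks at 5 and 10 to finish before stage 2 opens.

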We have reviewed the 8 patients treated thus far, and determined that 1 of those 8 patients would not be eligible per the current proposed revised criteria due to extensive ($\geq 5\%$ Total Body Surface) skin lesion and will be replaced. As such, the overall sample size will be increased to 36 by one more patient. The afore mentioned one patient that is still evaluable for toxicity and efficacy in the overall end analysis, but not as a part of the evaluation for the 13 patients treated in the first stage. The above two-stage design statistical analysis plan will not change.

The operating characteristics of the trial are given as follows. When the true response rate is 5% the probability of stopping the trial early is 51% and the probability of claiming the regimen to be promising is 8.4%. On the other hand, if the response rate is 20%, the probability to stop the trial early is 5% and the probability of claiming the regimen to be promising is 90%. The

expected sample sizes are 23.7 and 33.8 when the true overall response rates are 5% and 20%, respectively

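### The stated toxicity stopping probabilities and average numbers treated fit a 35-patient trial without the 11/35 limit, not the stated N=36 with seven limits; the probabilities are materially low only at true rates of 30% and 40%

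*Combined protocol and SAP*

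**What the plan says.** Section 13.1 (Statistical design) first sets out a two-stage response design in which, after 13 patients, "22 more patients will be enrolled to the study to reach a total of 35 treated patients". One treated patient is then to be replaced, so "the overall sample size will be increased to 36 by one more patient". The replaced patient is described as "one patient that is still evaluable for toxicity and efficacy in the overall end analysis". Section 5.0 also gives 36 as the maximum.

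The toxicity rule in the same section is applied "by cohorts of 5 patients for the whole patient population (N=36) for the first cycle". The model is binomial, where "p has a prior distribution of beta (0.20, 0.80"). The threshold is given as: "We consider that the probability of severe toxicity greater than 20% is excessive to the patients". The trial stops, with the treatment judged too toxic, once the posterior probability of a rate above 20% is at least 90%. The limits are 3/5, 4/10, 6/15, 7/20, 8/25, 10/30 and 11/35.

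The operating characteristics come from 5,000 simulations: 2% stopped and 34.5 treated on average at a true rate of 10%; 21% and 30.3 at 20%. At 30%, "the probability of stopping the trial early would be 62% with an average of 21.5 patients treated". At 40%, "then we will have a 91% chance to stop the trial early and with an average of only 13.5 patients treated".

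**The concern.** The paragraph states N=36 and seven limits, but at a 10% true rate it gives an average of 34.5 patients with only 2% of trials stopped. If 98% of trials run to 36, the average should be near 35.5. That suggests the figures describe a different design from the one printed beside them.

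The second sign is the 11/35 limit. In a 35-patient trial, the look at 35 comes after the last patient and might reasonably not be called an early stop. In a 36-patient trial it comes before the last patient, and the text stops the trial there as too toxic. It therefore belongs in the stated stopping probability.

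This is the plan's only numeric trial-level toxicity rule. These figures are all a reader has for judging how it performs.

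**Working it through.** **Inputs, all from section 13.1.** Cohorts of 5; limits 3, 4, 6, 7, 8, 10, 11 at 5, 10, 15, 20, 25, 30, 35 patients; prior beta(0.20, 0.80); threshold 20%; cut-off 90%; 5,000 simulations; N of 35 or 36.

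**Step 1: the limits.** With x events in n patients the posterior is beta(0.20 + x, 0.80 + n − x). The smallest x giving P(p > 0.20) ≥ 0.90 is 3, 4, 6, 7, 8, 10 and 11 at the seven looks. At n=35, for example, 10 events give 0.871 and 11 give 0.936. The listed limits are therefore correct if read as 'at or above'. The strict 'exceeds' reading, with seven limits and N=36, gives 8.6%, 45.7% and 85.6% at true rates of 20, 30 and 40%, far from the stated figures.

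**Step 2: reproduce the stated figures.** Use an exact binomial recursion: at each look add a binomial(5, p) count to the paths still running, remove those at or above the limit, and count paths never stopped as N patients. Entries are probability of stopping / average treated.

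| True rate | Stated | N=35, looks at 5 to 30 | N=36, all seven limits |
|---|---|---|---|
| 10% | 2% / 34.5 | 2.0% / 34.49 | 2.0% / 35.47 |
| 20% | 21% / 30.3 | 20.8% / 30.34 | 21.8% / 31.12 |
| 30% | 62% / 21.5 | 61.1% / 21.69 | 65.3% / 22.03 |
| 40% | 91% / 13.5 | 90.6% / 13.66 | 93.5% / 13.73 |

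All eight stated values fit the N=35, six-look column within rounding and simulation error.

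**Step 3: what moves the probabilities.** The chance of first stopping at the 35-patient look is 0.0001, 0.0105, 0.0422 and 0.0294 at the four rates. At 30%, 0.6112 + 0.0422 = 0.6534; at 40%, 0.9057 + 0.0294 = 0.9351. Seven looks with N=35 give these same probabilities, so the 36th patient changes none of them. The whole gap is the omitted 11/35 limit.

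**Step 4: what moves the averages.** Raising N from 35 to 36 adds one patient for every trial not stopped, so the average rises by 1 minus the stopping probability:

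- 10%: 34.49 + 0.98 = 35.47
- 20%: 30.34 + 0.78 = 31.12
- 30%: 21.69 + 0.35 = 22.03 (from unrounded values)
- 40%: 13.66 + 0.06 = 13.73 (from unrounded values)

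Leaving out the 35-patient look while keeping N=36 gives 35.47, 31.13, 22.07 and 13.76. The stated averages at 10% and 20% are thus wrong for N=36 whichever way that look is counted.

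**Step 5: simulation error.** For a probability the standard error is √(P(1 − P)/5000), with P taken from the written rule.

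- 30%: √(0.653 × 0.347/5000) = 0.67 point. After allowing half a point for rounding, (65.3 − 62.5)/0.67 = 4.2 standard errors.
- 40%: √(0.935 × 0.065/5000) = 0.35 point. Likewise (93.5 − 91.5)/0.35 is about 5.8 standard errors, using unrounded values.
- 20%: the gap is 0.8 point against a standard error of 0.58, about 1.4 standard errors.

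For an average, the standard error is the standard deviation of the number treated divided by √5000 = 70.7.

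- 10%: 3.82/70.7 = 0.054; gap 0.97, about 18 standard errors.
- 20%: 10.06/70.7 = 0.142; gap 0.82, about 5.8.
- 30%: 12.54/70.7 = 0.177; gap 0.53, about 3.0. Of that gap 0.35 is the change in N, and the other 0.19 (21.5 against 21.69) is simulation error.
- 40%: 9.63/70.7 = 0.136; gap 0.23, about 1.7, so within simulation error.

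**The case against.** The strongest defence is the word early. The plan reports the chance of stopping early, and in a 35-patient trial a look at 35 spares nobody, so leaving it out is reasonable. Even with N=36 it spares at most one patient. Section 13.1 states no pause in accrual between toxicity cohorts, and with the second dose on day 22 (section 6.1) the first cycle takes about three weeks to observe, so the 36th patient may already have been treated.

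The convention stands for N=35. It does not carry over to N=36 as written: the look precedes the last patient, the text says the trial is stopped and the treatment judged too toxic there, and nothing tells the reader that the look is excluded. Nor does it rescue the averages at 10% and 20%.

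Three stronger readings are tempting, and the documents do not support them.

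- A reader might infer that stopping is understated throughout. There is no gap at 10%, and the gap at 20% is within simulation error.
- A reader might infer that adding the 36th patient caused the low probabilities. It moves only the averages. That the figures were not updated when N rose is a plausible inference for those averages, but the plan does not say so.
- A reader might infer that the safety rule is weaker than claimed. The limits match the stated prior and cut-off, and the rule stops somewhat more often at high toxicity than the text says.

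**Conclusion.** The concern holds as a reporting error in the operating characteristics. The stated probabilities are low by 3.3 points at a true rate of 30% and 2.5 points at 40%. The averages are low by about 1.0 patient at 10% and 0.8 at 20%; the gap at 30% is partly simulation error, and the one at 40% cannot be told from it.

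This rests on three assumptions: limits read as 'at or above', which the posterior calculation supports; enrolment waiting for each look; and the toxicity rule considered by itself. The last matters because the two-stage design can also stop for no responses after 13 patients, with a stated probability of 51% when the response rate is 5%. Neither the stated nor the recomputed averages allow for that, so neither is the expected size of the whole trial.

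The importance is minor. No limit, enrolment figure or decision changes.

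**What to change.** In section 13.1, replace the figures with stopping probabilities of 2%, 22%, 65% and 94%, and averages of 35.5, 31.1, 22.0 and 13.7 patients, at true rates of 10, 20, 30 and 40%. Label them as N=36 with all seven limits, for the toxicity rule alone, ignoring the first-stage futility stop. Alternatively, keep the present figures and add that they are for N=35 with looks at 5 to 30 patients. Either way the cost is a few numbers or one clause, with no change to the limits, the rule or enrolment.
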